9.4 Treatment Period

The treatment period (or on-treatment period) is defined as from date of first administration of study treatment until 30 days after the last dose of study treatment or date of death, whichever is earlier.

10 STATISTICAL ANALYSIS METHODS

All tables and figures will be presented by cohort and overall. Since the interim analysis did not perform a homogeneity assessment of the primary endpoint, then the by-cohort and total groups will be presented for the efficacy endpoints.

10.1 Disposition of Subjects, Demographic and Baseline Data

10.1.1 Subject Disposition

Number (%) of patients will be presented by total patients only for All Screened Subjects, in the following:

- Screened (patients with informed consent) (number only)
- Screened but not enrolled and by reason for not enrolling

Number of patients will be presented for:

- Enrolled but not treated
- Treated

Number (% , calculated using denominator of treated patients) will be presented for

- End of treatment status (ongoing at data cut-off, discontinued) and by reason for treatment discontinuation
- End of study status (ongoing at data cut-off, discontinued) with reason for study discontinuation
- Subject in ITT, mITT, Safety, PP, PK population.

Number (%) of patients will be summarized in each analysis population (ITT, mITT, PP, SAF and PKP). Reasons for exclusion from PP will be provided:

- No measurable disease at baseline (inclusion criterion 7)
- No post-baseline disease assessment
- Violation of eligibility criteria at entry
- Treatment compliance <75%
- Other major protocol deviation that potentially affects efficacy assessment

Subjects per country and sites will be tabulated for the ITT, mITT and PP.

All subject disposition data will be presented in data-listings. Screening failure and reasons will be listed separately. Reason of exclusion from each analysis population will be listed.

10.1.2 Protocol Deviations

All deviations from the protocol will be reviewed and classified as minor, major or critical prior to the database lock for the main analysis. The full list of possible protocol deviations will be included in the study protocol deviation log which will include the classification.

Major (combined categories of major and critical) protocol deviations will be summarized by type of deviation, cohort and total in the ITT population. A by-subject listing of all protocol deviations will be presented and will include the type of deviation and description.

10.1.3 Demographic and Baseline Characteristics

Demographics and baseline characteristics will be summarized for the ITT, mITT and PP.

Demographic and baseline characteristics include:

- Age (years) at the time of consent, defined as (Informed consent date – date of birth+1) / 365.25. In case, the date of birth is not allowed to be collected due to local constraints, age entered in the eCRF will be used. Missing day of date of birth will be imputed as the 15th and missing month will be imputed as June.
- Gender, race, ethnicity and child-bearing potential (for females only).
- Height (cm), weight (kg), body mass index (kg/m^2) = weight / height².
- Eastern Cooperative Oncology Group (ECOG) Performance Status at baseline.

A by-subject listing showing the demographic characteristics will be provided.

10.1.4 Medical History

Medical history will be coded using the Medical Dictionary for Regulatory Activities (MedDRA) medical dictionary version 22.0 or later. Number (%) of subjects with medical history classified by system organ class (SOC) and preferred term (PT) will be summarized for the ITT, mITT and PP.

Medical history will be provided in a data-listing including the information on: SOC, PT, reported term, start and end date.

10.1.5 Disease Characteristics

Baseline disease characteristics will be summarized on ITT population. The analysis will be repeated on mITT and PP population.

Baseline disease characteristics include:

- Primary location of tumor.
- Histopathologic Grade
- Stage at initial diagnosis
- Initial Tumor-Node-Metastasis (TNM) stage.
- Time since initial diagnosis (years), defined as (treatment start date – initial diagnosis date)/365.25.
 - Missing day of initial diagnosis will be imputed at the 15th and missing month will be imputed as June. If the entire date is missing, date of initial diagnosis will be imputed as the earliest start date of prior anti-cancer therapy
- Site of local/metastatic disease
- Time since diagnosis of locally advance/metastatic disease (years), defined as (treatment start date – date of diagnosis of locally advance/metastatic disease) / 365.25.
 - Missing day of initial diagnosis will be imputed at the 15th and missing month will be imputed as June.
- FGFR fusion/alteration at screening (whether central lab or local lab) .

10.1.6 Prior anti-cancer treatments

Prior anti-cancer treatments will be summarized for the ITT, mITT and PP.

Number (%) of patients with prior anti-cancer treatments will be summarized for:

- Any prior treatment with radiotherapy.
- Any prior systemic therapy.
- Any prior surgery.
- Number of previous lines of anti-cancer systemic therapy as continuous and categorical (1, 2, 3, >3).

Prior anti-cancer treatments will be summarized by ATC level 2, 4 and WHO preferred name. Best response to last prior cancer systemic therapy will also be reported.

Additionally, prior anti-cancer treatments will be listed and will include:

- Prior radiotherapy: location, dose, start and end date, number of fraction days.
- Prior anti-cancer therapy: therapy agent, therapy class, intent of therapy, line number, start and end date, reason for therapy, best overall response reached.
- Prior surgery.

10.2 Efficacy Analyses

The efficacy analysis will be performed on the ITT population as the primary analysis. All efficacy analyses will be repeated on the mITT and PP population as supportive analysis, unless otherwise stated.

PA2 shortens the data collection period for efficacy data. Compared to early enrolled subjects, the later enrolled subjects will systematically have less tumor response assessments at PA2 implementation and time to event variables censored at date of last dose. There will be no additional statistical considerations to specifically address these systematic differences between earlier and later enrolled patients, and therefore, the planned statistical methods remain same as before PA2 was implemented.

Also, since the homogeneity assessment at interim analysis was not conducted, the efficacy endpoints will be analyzed and reported by cohort and pooled total subjects.

10.2.1 Objective Response Rate

Objective response rate (ORR) is defined as the proportion of subjects with a best overall response of confirmed PR or confirmed CR based on RECIST 1.1 criteria.

Best overall response (BOR) is defined as the best response designation for each subject that is recorded between the date of first administration of the study drug and the date of first documented disease progression per RECIST 1.1, the date of non-permitted concomitant treatment, date of a new systemic therapy or the date of study withdrawal for other reason, whichever occurs first.

Stable Disease (SD) will be considered as BOR only if the assessment is performed at least 6 weeks (i.e. 42 days) after the date of first dose of the study drug. If the minimum time from first dose of the study drug is not met when SD is observed, then subject's BOR depends on the subsequent assessments. A subject lost to follow-up after the first SD assessment will be considered not evaluable (NE). Subjects without any radiologic tumor assessment will be considered as NE. Patients who die with no evaluable RECIST assessments will be assigned to the NE category.

Per RECIST 1.1 criteria, CR and PR needs to be confirmed at a subsequent assessment, at least 4 weeks (i.e. 28 days) after initial overall response assessment of CR/PR. Confirmed BOR will be derived as described in RECIST 1.1 guidance summarized in Table 2.

Table 2 - Confirmation of BOR based on RECIST 1.1

Overall response first time point	Overall response subsequent time point*	Confirmed BOR
CR	CR	CR
CR	PR	SD, PD or PR ^a
CR	SD	SD, if minimum criteria for SD duration met at first time point. Otherwise PD
CR	PD	SD, if minimum criteria for SD duration met at first time point. Otherwise PD
CR	NE	SD, if minimum criteria for SD duration met at first time point. Otherwise NE
PR	CR	PR

Overall response first time point	Overall response subsequent time point*	Confirmed BOR
PR	PR	PR
PR	SD	SD
PR	PD	SD, if minimum criteria for SD duration met. Otherwise PD
PR	NE	SD, if minimum criteria for SD duration met. Otherwise NE
NE	NE	NE

*After the first post-baseline assessment of CR/PR, a subject may have fluctuations in target lesion assessment, but as long as they have a subsequent assessment showing response at least 4 weeks after the initial assessment without an assessment of progressive disease, this would qualify as an objective response. For instance, if a subject has PR-SD-PR or PR-NE-PR at consecutive tumour assessments, the objective response would qualify for PR.

^a If a CR is truly met at first time point, then any disease seen at a subsequent time point, even disease meeting PR criteria relative to baseline, makes the disease PD at that point (since disease must have reappeared after CR). Best response would depend on whether minimum duration for SD was met. However, sometimes ‘CR’ may be claimed when subsequent scans suggest small lesions were likely still present and in fact the subject had PR, not CR at the first time point. Under these circumstances, the original CR should be changed to PR and the best response is PR.

Subjects with a clinical progression determined by investigator will be scheduled to have a radiologic tumor assessment as per protocol. The response designation determined per RECIST 1.1 criteria using this scan will be included in the derivation of BOR. In case the planned scan is not performed, then the clinical progression will be used in the BOR derivation.

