### 3.3.2. Clinical data

The dose-escalation part of the first-in-human, multicenter, open-label study Phase I study of Debio 1347 (study Debio 1347-101) was recently completed. A total of 58 subjects with genomically activated advanced solid tumours were included and treated with Debio 1347 at doses from 10 to 150 mg/day. All were assessable for safety. Of these, 57 were evaluable for efficacy. Median treatment duration was 7.3 weeks (range 0.1 – 72).

All 58 treated subjects experienced  $\geq 1$  treatment emergent adverse event (TEAE) of which the highest severity was Grade 1 in 4 (6.9%), Grade 2 in 17 (29.3%), Grade 3 in 28 (48.3%), Grade 4 in 2 (3.4%) and Grade 5 in 7 (12.1%) subjects. The most common TEAEs with an incidence  $> 25\%$  were hyperphosphatemia, diarrhea, nausea, fatigue, constipation, decreased appetite and dry mouth. Nail changes (includes nail bed disorder, nail discoloration, nail dystrophy, onychalgia, onychoclasia and onychomadesis) were reported in 11 subjects. The most severe TEAEs were Grade 5 disease progression in 4 (6.9%) subjects and respiratory failure, sepsis and a new neoplasm (endometrial cancer) each in one subject (1.7%). They were not drug-related. Hyperphosphatemia, anemia, hyponatremia and dyspnea were most often severe (i.e., Grade  $> 2$ ). A total of 54 (93%) subjects experienced TEAEs considered as related to Debio 1347.

Twenty subjects experienced 39 serious adverse events (SAEs), most commonly dyspnea, but only two SAEs were deemed possibly study drug related and thus dose limiting toxicities (DLTs), i.e., Grade 3 hyperamylasemia (80 mg) and Grade 3 stomatitis (110 mg). DLTs occurred in 3 other subjects, i.e., Grade 2 dry mouth and eyes (60 mg) in one subject; Grade 3 asymptomatic hypercalcemia (80 mg); Grade 3 bilirubin increase and hyperphosphatemia (110 mg) in one subject. The subject with hyperamylasemia died from disease progression. The remaining 4 subjects recovered after Debio 1347 interruption and/or dose modification. As there were only  $\leq 2$  DLTs at the same dose level, the MTD (maximum tolerated dose) was not formally reached. No further dose-escalation was carried out.

Decreased left ventricular ejection fraction (LVEF) was reported in 1 subject (Grade 2) and 3 subjects experienced non-clinically significant Grade 1 (n = 2) and Grade 2 (n = 1) ECG QTc prolongation.

Overall, 21 subjects died from disease progression; no death was considered drug-related.

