#### 11.5.6. Efficacy

The ITT population will be the primary analysis population for efficacy analysis. Efficacy analyses will be repeated on the mITT population and the PP population as supportive analyses. The efficacy analysis will be conducted using centrally measured response as primary analysis and repeated on locally measured response as sensitivity analysis.

**Best overall response** is defined as the best confirmed response observed from first administration of study drug until disease progression. A PR or CR response needs to be confirmed in the following assessment performed at least 4 weeks later. For subjects who experience clinical progression, a radiological assessment will be performed to confirm the progression and the results of radiological assessment will be used in the efficacy derivation.

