However, the interim analysis to examine homogeneity of ORR across cohorts was not conducted after data monitoring review observed a lower than expected antitumor activity in the pooled group. Therefore, the main analysis will present the analysis of ORR (and other efficacy endpoints) by cohort and pooled total subjects.

Objective response rate will be summarized using frequencies and percentages. The Clopper-Pearson CI will be calculated using a one-sided binomial exact test at an alpha level as described in the hypothesis testing will be presented for all stage combined.

The best overall response (CR, PR, SD, PD and NE) will be summarized descriptively to show the number and percentage of subjects in each response category. The PD category will be further split into radiological progression (RECIST) and clinical progression. (Note: In case a patient has both radiological and clinical progression, the patient will be summarized under radiological progression.) The NE category will be further split into SD observed before 6 weeks, incomplete post baseline assessment and death without post-baseline assessment.

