10.2.5 Progression-Free Survival

Progression-free survival (months) is defined as (date of the first documented disease progression or death due to any cause, whichever occurs first - start date of treatment + 1)/30.4375.

The following censoring rule will be applied:

- Subjects who do not experience death or PD, nor initiate anti-cancer therapy will be right-censored at the date of their last adequate tumor assessment (i.e. a tumor assessment not showing NE).
- Subjects having initiated a new anti-cancer therapy before experiencing death or PD will be right-censored at the date of their last adequate tumor assessment prior to initiation of a new systemic therapy.
- Subjects who experienced death or PD after two or more consecutive missing or inadequate tumor assessments will be right-censored at their latest adequate assessment before death or PD.
- Subjects without a baseline or post-baseline assessment will be right-censored at the date of first administration of the study drug.

Progression-free survival rate at every 6 months will be presented with the corresponding 95% CIs will be estimated using the K-M method. A K-M plot for PFS will be presented.

The analysis will be performed on PFS calculated based on IRC assessment of response on the ITT population as the main analysis. Supportive analyses will be performed using:

- IRC evaluation of response on mITT and PP populations.
- Investigator assessed response on ITT, mITT and PP populations.

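### Clinical progression with no post-baseline scan is both NE and PD under the best-overall-response rules, and PFS then censors the same subject at first dose

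*SAP*

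**What the plan says.** Three rules in the SAP apply to a subject with clinical progression and no post-baseline scan.

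- **BOR, first rule (SAP 10.2.1, before Table 2):** "Subjects without any radiologic tumor assessment will be considered as NE". No exception is given.
- **BOR, second rule (SAP 10.2.1, after Table 2):** "In case the planned scan is not performed, then the clinical progression will be used in the BOR derivation". SAP 10.2.1.1 shows that the intended result is PD: "The PD category will be further split into radiological progression (RECIST) and clinical progression". The same paragraph adds: "The NE category will be further split into SD observed before 6 weeks, incomplete post baseline assessment and death without post-baseline assessment".
- **PFS (SAP 10.2.5):** "Subjects without a baseline or post-baseline assessment will be right-censored at the date of first administration of the study drug". The event time runs to the "date of the first documented disease progression or death due to any cause, whichever occurs first - start date of treatment + 1". The main PFS analysis uses the independent review committee (IRC) read. The investigator-assessed version is supportive and shares the same censoring list.

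Protocol 11.5.6 has a confirming scan done after clinical progression and says "the results of radiological assessment will be used in the efficacy derivation". It does not say what happens if the scan is missed. The censoring list in Protocol 11.5.6.2 has no Day 1 rule and is introduced as covering subjects with neither documented progression nor death.

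**The concern.** Two programmers working from SAP 10.2.1 could put the same subject in different rows of the BOR table. If PD is chosen, that table shows a progression while the PFS analysis has the subject progression-free and censored at first dose. The primary BOR is also a central read, so an investigator's clinical call would enter a central RECIST category that the central PFS does not use.

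For PFS, these subjects would be censored because they are failing. Censoring them at Day 1 removes them from the risk set before any event, which raises every later point on the curve. No planned PFS analysis clearly counts them. In the investigator version the matter is open, because SAP 10.2.5 does not define documented progression and Protocol 8.4.1, in its treatment-stopping criteria, accepts progression documented by physical examination.

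**Working it through.** The plan states no figure on this point, so there is none to reproduce. The check applies the rules to cases and then sizes the PFS effect.

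**Step 1: the rules by case.**

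| Case | BOR | IRC PFS |
|---|---|---|
| Clinical progression, no post-baseline scan, alive | NE by the first rule, PD by the second | Censored at first dose |
| Same, then dies | Same conflict | Event by the definition; censored by the Day 1 rule, which has no exception for death |
| Qualifying SD scan, later clinical progression with no scan | SD, no conflict | Censored at that SD scan |

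The BOR conflict is therefore limited to subjects with no post-baseline scan. With the first on-treatment scan at the end of Cycle 2 (about week 8), these are in practice subjects who fail before then.

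**Step 2: response rates.** NE and PD are both non-responders and both outside disease control, and the ITT denominator is the same. ORR and DCR do not move. The PD and NE percentages each move by the full share f. DOR includes responders only, who have scans, so only its censoring date can be affected.

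**Step 3: PFS.** Let a share f fail clinically before the first scan, and let S_rest(t) be PFS in the others.

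- Counting the failures as events: S_true(t) = (1 − f) × S_rest(t), for t after those failures.
- Censoring them at Day 1: Kaplan-Meier estimates S_rest(t) = S_true(t)/(1 − f).

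The documents give neither f nor a PFS rate. Assume a true six-month PFS of 20%:

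| Assumed f | Reported six-month PFS |
|---|---|
| 0% | 20.0% |
| 5% | 20/0.95 = 21.1% |
| 10% | 20/0.90 = 22.2% |
| 20% | 20/0.80 = 25.0% |

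**Step 4: simulation check.** N = 63 (the pooled number at the second IDMC meeting, SAP 10.8.2), 1,000 runs. Assumptions: early failures uniform between 0.5 and 1.8 months, the others exponential with a 4-month median, administrative censoring at 12 months.

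| Unscanned failures | Six-month PFS, counted → censored Day 1 | Median in months, counted → censored | Ratio of rates |
|---|---|---|---|
| 3/63 (4.8%) | 33.8% → 35.5% | 3.78 → 3.96 | 1.05 |
| 6/63 (9.5%) | 32.0% → 35.4% | 3.46 → 4.06 | 1.105 |
| 13/63 (20.6%) | 28.1% → 35.4% | 2.73 → 3.95 | 1.26 |

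The ratios equal 1/(1 − f). Assumed medians of 2.5 and 6 months for the others gave the same ratios.

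**The case against.** **The specific rule should override the general one.** On this view the result is PD, as the PD clinical-progression row suggests. That is the likelier reading, but it is not written down, and the NE sub-row for incomplete assessment also fits the subject. It would also leave an investigator's call inside a central RECIST table.

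**The group may be empty.** This stands. Protocol 8.2.2.1.2 requires CT or MRI in all subjects at progression and/or end of treatment, so the case needs a missed mandatory scan. A reader might infer from Protocol 3.3.2 ("Median treatment duration was 7.3 weeks") and a first scan at week 8 that the group is large. The documents do not support that. In the same Phase I study, 57 of 58 subjects were evaluable for response (35 PD + 16 SD + 6 PR = 57), although it is not stated whether any of those PDs were clinical only.

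**The inflation factor is a ceiling.** This also stands. It assumes that no later death or progression of these subjects counts as an event. Before Amendment 2, off-treatment subjects without progression were followed every 12 weeks for disease status and survival, so some later events might count. At f = 5% the shift is 1.1 points, against a 95% half-width of 1.96 × √(0.20 × 0.80/63) = 9.9 points.

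**Other readings that go too far.** A reader might say the subject is counted three ways. Only NE versus PD is a conflict within one endpoint; Day 1 censoring belongs to another endpoint and is consistent with NE. A reader might also see Protocol 11.5.6 as contradicting the SAP, but it presupposes the scan and is silent without one. Leaving clinical progression out of an IRC-based PFS is a defensible convention. The SAP's modification history discusses the BOR sentence, but it is a change log and nothing here rests on it.

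**Conclusion.** The point holds as a defect in the rules. For a subject with clinical progression and no post-baseline scan, BOR is NE or PD with no stated precedence. PFS is censored at first dose, the rule clashes with death being an event, and documented progression is undefined.

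The outputs affected are the PD/NE split and PFS, with a lesser effect on the DOR censoring date; primary ORR and DCR are not affected. If such subjects exist and have no later counted event, the direction of the PFS error is upward, by at most 1/(1 − f): 1.05 to 1.25 for an assumed f of 5% to 20%. It does not follow that the trial's PFS is in fact biased, because the documents do not give f and the effect is zero if all required scans were done. PFS is a secondary endpoint with no planned test and enrolment has been halted, so this is a correction worth making before database lock rather than a threat to the main conclusion.

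**What to change.** 1. **BOR.** Restrict the clinical-progression sentence in SAP 10.2.1 to investigator-assessed BOR, where it gives PD, and make the NE sentence yield to it there. Keep central RECIST BOR as NE, with its own sub-row for clinical progression without a scan. Show the PD clinical-progression row of SAP 10.2.1.1 only in the investigator table. Simply deleting the sentence would remove the only basis for PD in the investigator read and leave that row unexplained.
2. **Event definition.** Define documented progression separately for IRC and investigator PFS and DOR.
3. **Day 1 rule.** Limit it to subjects without a documented death, in line with the scope stated in Protocol 11.5.6.2, and say how it interacts with the rule on two or more missed assessments.
4. **Sensitivity.** Keep IRC PFS as the main analysis. Add one run of PFS and DOR that counts clinical progression without a scan as an event on its date, and report the number of such subjects.

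The cost is SAP wording and minor programming. No new data collection should be needed, since the SAP already plans to tabulate clinical progression; that its date is recorded is an assumption to confirm. PFS in the sensitivity run may be slightly less favourable.
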